6.1.1. Administration Details

Part A and Part B: LY3872386 Administration

In IV dosing cohorts, LY3872386 will be administered as a slow IV infusion over approximately to minutes. Resuscitation equipment, emergency drugs, and appropriately trained staff must be available while the participant is staying at the investigation site.

In SC dosing cohorts, all LY3872386 injections will be administered into the SC tissue of the abdominal wall. Injection sites will be alternated between 4 sites (that is, right and left upper quadrants and the right and left lower quadrants) on the abdominal wall (where applicable). Whenever possible, study drug administration should be carried out by the same personnel.

Part C: Prednisone Administration

All doses of prednisone will be administered with approximately mL of room temperature water while in a sitting position.

Prednisone tablets should be swallowed whole. Participants should not break, crush, or chew the study intervention.

On dosing days, participants will adhere to meal restrictions as outlined in Section 5.3.1.

6.1.2. Premedication for Infusions

Premedication for the infusions is not planned. However, if an infusion reaction occurs, appropriate medication may be used as determined by the study investigator(s). If infusion reactions are observed, but review of the data suggests that dose escalation may continue, administration of acetaminophen 500 to 1000 mg and/or an antihistamine may be administered orally 30 to 60 minutes prior to the start of infusion for subsequent participants.

The decision to implement premedication for infusions in subsequent cohorts will be made by the investigator and the sponsor, and recorded in the study documentation, along with the doseescalation decision.

Any premedication given will be documented as a concomitant therapy (see Section 6.9).

6.1.3. Management of Infusion Reactions

There is a risk of an infusion reaction with any biological agent. Therefore, all participants should be monitored closely.

Symptoms and signs that may occur as part of an infusion reaction include, but are not limited to:

- fever
- chills
- nausea
- headache
- bronchospasm
- hypotension
- angioedema
- throat irritation
- rash
- pruritus
- myalgia, and
- dizziness.

In the event that a significant infusion reaction occurs, the following guidance should be followed:

• The investigational product infusion should be slowed (for example, reduce the infusion rate by 50% [for example, an infusion rate of 12 mL/h becomes 6 mL/h or slower]) or stopped, depending on the symptoms/signs present:

o if slowed, the infusion should be completed at the slower rate, as tolerated, and

- o if determined by the investigator that the infusion should no longer continue, no further attempts to dose the participant should be made.
- Supportive care should be employed in accordance with the symptoms/signs and consistent with local guidelines.
- If a participant's infusion reaction is sufficiently severe to discontinue the infusion, subsequent infusions may be administered with premedication at the discretion of the investigator, following agreement with the Lilly CRP or clinical pharmacologist
- If a participant's infusion rate is reduced due to an infusion reaction, subsequent infusions may be administered at the discretion of the investigator, following agreement with the Lilly CRP or clinical pharmacologist. If further infusions are administered, the infusion rate must not exceed the slowest rate used to complete the infusion on the occasion when the infusion reaction occurred. Premedication may be administered at the discretion of the investigator.
- If it is determined that the participant should not receive further doses of the investigational product, the participant should complete AE and other follow-up procedures per the SoA (Section 1.3) of this protocol.

6.2. Preparation, Handling, Storage, and Accountability

The investigator or designee must confirm appropriate storage conditions have been maintained during transit for all study intervention received and any discrepancies are reported and resolved before use of the study intervention.

Only participants enrolled in the study may receive study intervention. Only authorized study personnel may supply, prepare, or administer study intervention.

All study intervention must be stored in a secure, environmentally controlled, and monitored (manual or automated) area in accordance with the labeled storage conditions with access limited to the investigator and authorized study personnel.

The investigator or authorized study personnel are responsible for study intervention accountability, reconciliation, and record maintenance, that is, receipt, reconciliation, and final disposition records.

Further guidance and information for the preparation, handling, storage, and final disposition of unused study interventions are provided in the Pharmacy Manual/Pharmacy Preparation Instructions.

Where applicable, the study intervention will be prepared by an unblinded pharmacy staff or a pharmacist who is not involved in any other study-related procedures.

6.3. Assignment to Study Intervention

For Part A and Part B, this is a double-blinded, randomized study of LY3872386 in healthy participants and in patients with AD. For Part C, this is an open-label study of prednisone in healthy participants.

6.4. Blinding

6.4.1. Part A: Single-Ascending Dose of LY3872386

This is a double-blind study in which participants and investigators are blinded to the study intervention. Emergency codes regarding treatment assignment will be available to the investigator, and in case of an emergency, the investigator has the sole responsibility for determining if unblinding of a participant's intervention assignment is warranted. Participant safety must always be the first consideration in making such a determination. If the investigator decides that unblinding is warranted, the investigator should make every effort to contact the sponsor to discuss the situation prior to unblinding a participant's intervention assignment, unless this could delay the emergency treatment for the participant. If a participant's intervention assignment is unblinded, the sponsor must be notified within 24 hours of this occurrence.

Investigators will remain blinded to each participant's assigned study intervention throughout the course of the study. To maintain this blind, an otherwise uninvolved third party will be responsible for the reconstitution and dispensation of all study interventions and will endeavor to ensure that there are no differences in the time taken to dispense following the randomization.

In the event of a quality assurance audit, the auditor(s) will be allowed access to unblinded study intervention records at the site(s) to verify that randomization/dispensing has been done accurately.

If an investigator, site personnel performing assessments, or participant is unblinded, the participant must be discontinued from the study. In cases where there are ethical reasons to have the participant remain in the study, the investigator must obtain specific approval from a sponsor CRP for the participant to continue in the study.

6.4.2. Part B: Multiple-Ascending Dose of LY3872386

For MAD Part B only, all participants will be centrally assigned to the randomized study intervention using an IWRS. Before the study is initiated, log-in information and directions for the IWRS will be provided to each site. IWRS will not be used for the dispensing of study intervention and will only be used for randomization.

This is a double-blind study in which participants and investigators are blinded to the study intervention. The IWRS will be programmed with blind-breaking instructions. In case of an emergency, the investigator has the sole responsibility for determining if the unblinding of a participant's intervention assignment is warranted. Participant safety must always be the first consideration in making such a determination. If the investigator decides that unblinding is warranted, the investigator should make every effort to contact the sponsor to discuss the situation prior to unblinding a participant's intervention assignment, unless this could delay emergency treatment for the participant. If a participant's intervention assignment is unblinded, the sponsor must be notified immediately within 24 hours of this occurrence. The date and reason that the blind was broken must be recorded.

6.4.3. Part C: Open-Label of Prednisone

This is an open-label study.

6.5. Study Intervention Compliance

The study intervention will be administered under medical supervision by the investigator or designee. The dose of the study intervention and study participant identification will be confirmed prior to the time of dosing. The date and time of each dose administered will be recorded in the source documents and will be provided to the sponsor as requested.

6.6. Dose Modification

6.6.1. Dose Decision/Escalation

By nature of being a dose-escalation study, data will be evaluated on an ongoing basis.

[figure not shown]
Safety data, in particular AEs, SAEs, and laboratory abnormalities, will be independently assessed by the investigator.

[figure not shown]
Safety and tolerability data will be the primary criteria for the dose escalation in Part A (SAD of LY3872386) and Part B (MAD of LY3872386) (Section 8.2).

[figure not shown]

After review of these data, an agreement on the appropriate dose will be made by the investigator and sponsor for the next cohort/dose level. The magnitude of dose escalations may be reduced following data review,

No dose decision can occur without prior discussion and agreement between the investigators and the sponsor.

6.7. Continued Access to Study Intervention after the End of the Study

LY3872386 and prednisone will not be made available to participants after the conclusion of the study.

6.8. Treatment of Overdose

For this study, an overdose of LY3872386 or prednisone is considered any dose higher than the dose assigned through randomization. Treatment for overdose is the best supportive care.

The sponsor does not recommend specific treatment for an overdose.

In the event of an overdose, the investigator/treating physician should

- contact the Lilly Clinical Pharmacologist immediately
- evaluate the participant to determine, in consultation with the medical monitor, whether the study intervention should be interrupted or the dose should be reduced
- closely monitor the participant for any AE/SAE and laboratory abnormalities for approximately 12 weeks or 5 half-lives (whichever is longer)

- obtain a blood sample for PK analysis if requested by the Lilly Clinical Pharmacologist (determined on a case-by-case basis), and
- document the quantity of the excess dose as well as the duration of the overdose in the CRF.

6.9. Prior and Concomitant Therapy

Any medication or vaccine (including over-the-counter or prescription medicines, vitamins, and/or herbal supplements or other specific categories of interest) that the participant is receiving at the time of enrollment or receives during the study must be recorded along with

- reason for use
- dates of administration, including start and end dates, and
- dosage information, including dose and frequency for concomitant therapy of special interest.

The medical monitor should be contacted if there are any questions regarding concomitant or prior therapy.

In general, concomitant medication should be avoided. The use of chronic, stable doses of thyroid hormone, or hormone replacement therapy is allowed. Acetaminophen (1 g, maximum 4 g/24 hours) may be administered at the discretion of the investigator for the treatment of headache and so on. Antihistamine may be administered as a premedication for infusion at the discretion of the investigator. Other concomitant medications may be considered on a case-by-case basis by the medical monitor in consultation with the Lilly CP/CRP or designee. If the need for concomitant medication (other than acetaminophen) arises, the inclusion or continuation of the participant may be at the discretion of the investigator after consultation with the sponsor. Any medication used during the course of the study must be documented.

For AD therapies permitted as part of rescue therapy see below.

6.9.1. Rescue Medicine

Criteria for rescue therapy initiation

• Investigators should attempt to manage participants with emollients. However, investigators are allowed to rescue participants who are experiencing unacceptable or worsening symptoms of AD after Week 8. Prior to rescue, it is recommended that an increased frequency of emollient use is attempted to at least twice a day or more in an effort to control symptoms. The rationale for rescue will be documented.

Choice of rescue therapy treatment

- Triamcinolone 0.1% cream and/or hydrocortisone 2.5% ointment. In the event that providing 1 or both of these topical formulations is not possible, an alternate, equivalent potency TCS cream and/or ointment may be provided.
 - o Commercially available triamcinolone 0.1% cream and/or hydrocortisone 2.5% ointment may be supplied by the clinical site.

• Investigators may elect to use TCNIs and/or crisaborole where approved, although use of either of them during the study is not encouraged. If TCNIs are prescribed, use should be limited to problem areas only (for example, face, neck, skin folds, and genital areas).

- On the days of study visits, topical therapy should not be applied before the participant
 has undergone all study procedures and clinical evaluations to allow adequate assessment
 of skin dryness.
- Participants receiving topical therapy will remain on the study and continue to take IP. The use of rescue therapy will be documented in the eCRF.

In participants who do not improve sufficiently with the provided rescue topical therapy after 7 days, a higher potency TCS may be used, and IP may continue. It is recommended that if a participant achieves "clear" to "almost clear" skin after topical rescue, medium- and/or high-potency TCSs and TCNIs should be stopped, and low-potency TCSs (for example, hydrocortisone 2.5% ointment) should be used once daily for an additional 7 days, then stopped. If lesions return, participants can be retreated with TCSs with or without TCNIs and/or crisaborole as before, at the discretion of the investigator.

If topical rescue therapy as described above fails to sufficiently control AD symptoms, then oral systemic medications may be used as rescue (for example, corticosteroids, cyclosporine, and methotrexate). However, IP will be required to be permanently discontinued for the remainder of the 12-week study duration. If these medications are needed for other medical conditions (for example, asthma flare), they will still be treated as rescue medications.

Investigators should make every attempt to conduct efficacy and safety assessments immediately before administering any rescue treatment. An unscheduled visit can be used for this purpose if necessary.

7. Discontinuation of Study Intervention and Participant Discontinuation/Withdrawal

Participants discontinuing from the study intervention prematurely for any reason should complete AE and other follow-up procedures per Section 1.3 of this protocol.

Discontinuation of specific sites or of the study as a whole are handled as part of Appendix 1 (Section 10.1).

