2.3. Benefit/Risk Assessment

The toxicology data for LY3872386 demonstrate an acceptable nonclinical safety profile and margin of safety to support the transition from preclinical status to a clinical single-dose study in healthy participants and a multiple-dose study in patients with AD.

The nonclinical safety profile of LY3872386 is generally consistent with its intended pharmacology. Primary safety concerns predicted from studies with the ADC and the payload are bacterial and other infections, secondary to decreases in lymphoid tissue lymphocytes and circulating blood lymphocytes. Other potential risks identified for LY3872386 in toxicology studies and consistent with GC pharmacology are

- atrophy of skin hair follicles, especially near SC injection sites, potentially leading to thinning hair or hair loss
- suppression of the HPA axis
- increased serum triglycerides, and
- increased serum glucose.

The safety and efficacy associated with modulation of the IL-4/IL-13/IL-4R axis have been evaluated with approved drugs such as dupilumab and tralokinumab, and the safety and efficacy of GCs as a class are well-established. The key safety concerns and PD effects of LY3872386, including infection, conjunctivitis, hypersensitivity reactions, local injection site reactions, and systemic GC exposure from LY3558533 (free payload), will be closely monitored during the clinical study.

As with other immunomodulatory therapies, LY3872386 and prednisone may increase the risk of developing infections, increase the risk of an infection becoming more serious, and/or change the effectiveness of vaccines administered. LY3872386 may also increase the risk of opportunistic infections and the reactivation of latent infections. Participants will therefore be screened for hepatitis B, hepatitis C, HIV, and TB. In addition, all participants should be monitored for symptoms and signs of infection after administration of LY3872386 or prednisone.

Infusion reactions and hypersensitivity reactions are potential risks for all biologics. These risks will be carefully monitored during the dosing period in Parts A and B (the LY3872386 portions of the study), with close observation after infusion and stopping rules that prevent re-challenge of patients/participants with significant hypersensitivity reactions.

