 - d. Have used any of the following topical medications within 1 week prior to randomization (Visit 2):
 - topical corticosteroids or topical immune modulators (for example, tacrolimus or pimecrolimus)

Note: pimecrolimus may not be available in all regions, including Japan.

- topical phosphodiesterase type 4 inhibitor, or
- topical Janus kinase inhibitor.

Note: Intranasal or inhaled steroid use is allowed during the trial.

- 46. have received the following excluded medications/treatments within 4 weeks prior to randomization (Visit 2) or plan to use during the study:
 - a. oral systemic corticosteroids and leukotriene inhibitors.
 - b. systemic immunomodulators, including, but not limited to, cyclosporine, methotrexate, mycophenolate mofetil, azathioprine, and Janus kinase inhibitors (such as tofacitinib, ruxolitinib, baricitinib, upadacitinib or abrocitinib).
 - c. sedating antihistamines including, but not limited to, alimemazine, chlorphenamine, clemastine, cyproheptadine, diphenhydramine, hydroxyzine, ketotifen, and promethazine.

Note: Participants may use newer, less sedating antihistamines (for example, fexofenadine, loratadine, and cetirizine).

d. any other systemic therapy used to treat AD or symptoms of AD (approved or off-label use).

- e. phototherapy, including therapeutic phototherapy (psoralen plus ultraviolet-A and ultraviolet-B), excimer laser, or tanning beds.
- 47. patients with a positive beta-D-glucan test at screening and a confirmed diagnosis of pneumocystis pneumonia will be excluded.
- 48. have experienced hypersensitivity to the active substance or to any of the excipients.
- 49. For Japanese participants only: have evidence of, or a positive test for, HBV infection, defined as:
 - a. positive for hepatitis B surface antigen (HBsAg), or
 - b. positive for hepatitis B core antibody (HBcAb) and positive HBV DNA, or
 - c. positive for hepatitis B surface antibody (HBsAb) and positive for HBV DNA.

Note: Patients who are positive for HBcAb or HBsAb and negative for HBV DNA may be enrolled in Part B of the study. In this case, repeat testing for HBV DNA is required at least once every month during the study.

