10.6.2 Concomitant medication

Concomitant medication will be coded using the WHO drug dictionary (version is documented in the DMP). Concomitant medication will be listed.

CONFIDENTIAL Protocol Reference: J4L-MC-KMAA

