10.7.2 Efficacy Statistical Methodology

Descriptive statistics

CONFIDENTIAL
Protocol Reference: J4L-MC-KMAA

Analysis of covariance (ANCOVA)

The mean percent change from baseline CCl data will be analyzed on Weeks 1 and 12 by an ANCOVA model with baseline as a covariate and treatment as a fixed effect to estimate the LS means and corresponding 90% CIs.

Example SAS code for the ANCOVA:

proc mixed data=saf1 method=reml;
 by param1;
 class treatment;
 model change = base treatment / residual cl alpha=0.1 ddfm=kr2;
 lsmeans treatment / alpha=0.1 cl pdiff;
 ods output lsmeans=lsmeans1 diffs=diff;
run;

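### Part B efficacy is modelled at Week 12, after corticosteroid rescue opens at Week 8, and late HPA tests share that exposure; add a Week 8 ANCOVA and displays by rescue exposure

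*Protocol*

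**What the plan says.** **Rescue (Protocol 6.9.1).** "investigators are allowed to rescue participants who are experiencing unacceptable or worsening symptoms of AD after Week 8". The first choices are topical corticosteroids; topical calcineurin inhibitors and crisaborole are possible but not encouraged. Under topical rescue, "Participants receiving topical therapy will remain on the study and continue to take IP", and if the response after 7 days is not sufficient, "a higher potency TCS may be used, and IP may continue". If topical rescue fails, oral systemic drugs, including corticosteroids, may be given, but then "IP will be required to be permanently discontinued for the remainder of the 12-week study duration". Investigators are asked to try to assess efficacy and safety immediately before any rescue, at an unscheduled visit if needed. Rescue use goes into the eCRF.

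**Efficacy model (SAP 10.7.2).** Percent change from baseline (the variable is redacted) "data will be analyzed on Weeks 1 and 12 by an ANCOVA model with baseline as a covariate" and treatment as a fixed effect, giving least-squares means and 90% confidence intervals. SAP 10.7.1 sets the population as mITT. Protocol 9.3.4.1 rules out efficacy hypothesis tests.

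**Rescue in the SAP.** The visible text does not mention it. SAP 10.6.2 says "Concomitant medication will be listed". Protocol 9.3.1 leaves missing-data methods to the SAP; SAP 14.2 holds only a display rule for listings.

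**HPA axis.** Protocol 2.3 names "suppression of the HPA axis" among the potential risks. In Part B, a failed cosyntropin response is a criterion for permanent discontinuation (Protocol 7.1.6.3).

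**The concern.** The efficacy model reads Part B at a time when patients who are doing badly may already be on topical corticosteroid. With no visible rule, all observed mITT values enter, and the Week 12 contrast compares LY3872386 plus any rescue with placebo plus any rescue. Week 8 (V6), the last scheduled visit before rescue for atopic dermatitis (AD) opens, has vIGA-AD, EASI, SCORAD and itch scores in both dosing schedules but is not a model time point.

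The second issue is attribution. The product carries a glucocorticoid payload, and the first-line rescue drugs are glucocorticoids. A late abnormal cosyntropin result could come from either source. If placebo patients receive more rescue steroid, a payload effect can be partly hidden in the comparison with placebo. In a rescued LY3872386 patient, a rescue effect can be read as a payload effect. The discontinuation criterion in Protocol 7.1.6.3 does not carry the qualifier about other obvious causes that 7.1.6.1 and 7.1.6.2 carry.

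At stake is the quality of estimates meant to guide later trials, not an error rate: nothing is formally tested.

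**Working it through.** **1. Visit days.** Study days are redacted in the Part B schedules, so I matched marked visits to the days named in the amendment summaries.
- HbA1c row: V1, V2, V4, V8, last follow-up, ED. Named: screening, Day 1, Day 29, Day 85, Day 183, ED. So V4 = Day 29 and V8 = Day 85.
- Ocular row adds V6 and V801; named days add Day 57 and Day 88. So V6 = Day 57.
- In the second schedule (1.3.2.2), the non-dosing visits V3, V5 and V7 match Days 15, 43 and 71. In the first (1.3.2.1) those days are not visible, but a single visit lies between Day 1 and Day 29; even spacing gives Day 15.
- Week 8 = 8 × 7 + 1 = Day 57. Week 12 = 12 × 7 + 1 = Day 85. No Week 1 visit appears.

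**2. Cosyntropin counts.** The blood-volume tables (Protocol 10.2.1.2 and 10.2.1.3) give 10 tests and 6 tests, each with 3 draws of 2 mL: 10 × 3 × 2 = 60 mL and 6 × 3 × 2 = 36 mL, as stated. The row label in the schedules is redacted. Counting marked visits without ED reproduces the labelled totals for PK (22 and 20) and immunogenicity (6 and 11). Only one unlabelled row, the last before the ocular row, gives 10 and 6.

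| Schedule | Tests at | After Day 57 | Treatment period, after Day 57 | Follow-up |
|---|---|---|---|---|
| 1.3.2.1 | V2–V8, V802–V804 | 5 of 10 | V7, V8: 2 of 7 (29%) | 3 |
| 1.3.2.2 | V2, V4, V6, V8, V803, V805 | 3 of 6 | V8: 1 of 4 (25%) | 2 |

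**3. Efficacy distortion, illustration only.** Let D be the true contrast, rP and rA the shares rescued on placebo and active, and g the gain from rescue, taken as equal in both arms. Then observed contrast = D − (rP − rA) × g. The documents give none of these. Assume D = 30 percentage points and g = 15, 30 or 45.

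| rP | rA | Observed contrast (g = 15 / 30 / 45) | Change from 30 |
|---|---|---|---|
| 20% | 5% | 27.75 / 25.5 / 23.25 | −7.5% / −15% / −22.5% |
| 40% | 10% | 25.5 / 21 / 16.5 | −15% / −30% / −45% |
| 50% | 10% | 24 / 18 / 12 | −20% / −40% / −60% |
| 20% | 20% | 30 / 30 / 30 | none |
| 10% | 30% | 33 / 36 / 39 | +10% / +20% / +30% |

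**4. HPA confounding, illustration only.** Let a be the payload's abnormal-test rate and s the chance that rescue steroid causes an abnormal test. Active = a + (1 − a) × rA × s; placebo = rP × s. Assume a = 15%, rA = 10%, rP = 40%.
- s = 5%: (0.15 + 0.85 × 0.10 × 0.05) − 0.40 × 0.05 = 0.134.
- s = 20%: (0.15 + 0.85 × 0.10 × 0.20) − 0.40 × 0.20 = 0.087.
- The true difference of 15 points shrinks to between 13.4 and 8.7.
- With no payload effect (a = 0), active would still show rA × s = 0.5% to 2% abnormal tests.
- With rA = 30% and rP = 10%, the 15-point difference grows to between 15.8 and 18.1.

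**The case against.** **Redaction.** A reader might infer that the SAP has no rule for rescue. The documents do not support that. SAP 10.6.10 to 10.6.13 are absent from the public text, 10.4.2 is partly blacked out, nothing can be read under the descriptive-statistics label in 10.7.2, and Protocol 9.3.4.1 breaks off in mid-account of binary outcomes. Any of these could hold a rule. What can be said is that the visible ANCOVA statement and code contain none. This stands.

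**All-observed analysis is legitimate.** Using every mITT value regardless of rescue estimates a treatment-policy effect, and efficacy is exploratory. This stands too, so the all-observed result should stay. A reader still needs the amount of rescue by arm to interpret it.

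**Half the tests is not half the on-treatment evidence.** Most post-Day 57 cosyntropin tests (3 of 5 and 2 of 3) are follow-up. Within treatment, 5 of 7 and 3 of 4 come before AD rescue opens. That is right, and it limits the HPA part. Follow-up tests are not immune, because 6.9.1 gives no end date for topical rescue.

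**Mitigation already exists.** Pre-rescue assessments are requested and emollient step-up is recommended first. That helps, but only if the analysis uses those assessments, and no visible text does.

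**Dropping rescued patients may be worse.** This stands. For rescue confined to placebo at rate r, the all-observed dilution is r × gain; exclusion dilutes by r × (mean of non-rescued minus mean of rescued without rescue). If that gap exceeds the gain, exclusion is the more biased choice.

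**Inhaled and intranasal steroids.** "Intranasal or inhaled steroid use is allowed during the trial" applies to both randomized arms and is no differential bias by design.

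**Conclusion.** The point holds in limited form. Week 12 is the only model time point with visible scheduled data, and it falls four weeks after AD rescue may start. The contrast there can be distorted. A reader might infer a certain bias toward the null; that needs placebo to be rescued more. It is zero at equal rescue and equal benefit, and it reverses if active is rescued more. The assumed grid runs from a 60% loss to a 30% gain, but no real size can be computed: Part B numbers and allocation are redacted and rescue rates are not given.

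A reader might also infer that dosing continues under every kind of rescue. It does so only under topical rescue; oral systemic rescue requires study drug to stop.

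For the HPA axis, rescue steroid can mask or mimic a payload effect in 5 of 10 and 3 of 6 tests at most. Only 2 of 7 and 1 of 4 treatment-period tests are exposed. This rests on identifying a redacted row, on visit days taken from the amendment summaries, and on topical absorption that the documents do not quantify.

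**What to change.** Change the SAP only and leave the rescue rules as they are. If redacted text already covers any item, cross-refer to it.

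1. **Add Week 8 (V6, Day 57) to the ANCOVA**, same model, beside Week 12. It is the last scheduled visit before AD rescue is allowed. It is not guaranteed steroid-free, since systemic drugs for other conditions count as rescue whenever given. It also follows fewer doses than Week 12 (doses at visits before V6 against before V8: 4 against 6 in the first schedule, 2 against 3 in the second), so it complements Week 12 and does not replace it.
2. **Week 12.** Keep the all-observed result and report the number rescued by arm, topical and oral separately. As a supplementary analysis, use the last assessment before first rescue for continuous scores and count rescued patients as non-responders for binary outcomes. Do not simply exclude them.
3. **Cortisol and cosyntropin, Part B.** Keep the all-data summary as the main safety display. Add a by-arm display that flags or separates samples taken after corticosteroid rescue, using the recorded dates.

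The scores, tests and medication dates are already collected. The cost is some SAP wording, a few extra tables and one more exploratory estimate.
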